Rationale:

Electroencephalographic density spectral array (DSA) is a three dimensional method to display electroencephalogram (EEG) signals consisting of the EEG frequency (y-axis), the power of the EEG signal (colour-coded to be integrated into a two dimensional plot) and the development of the EEG power spectrum over time (x-axis). DSA is routinely used to measure depth of hypnosis (DoH) by a part of the staff members in our department. When DSA is used, dose adjustments of sevoflurane will be made based on monitoring depth of anaesthesia. However, most of our colleague do not use DSA. Dose adjustment is then based on (subjective) clinical surrogate parameters, or in general mostly based on a minimal alveolar concentration of the anaesthetic gas that is used.

Electroencephalographic DSA monitoring provides continuous objective information on DoH and should result in a faster speed of emergence and recovery from general anaesthesia (GA). This will be addressed in a randomised controlled trial.

Objective:

To evaluate the influence of DSA monitoring, provided by the NarcotrendTM monitor, on the speed of emergence and recovery from GA.

Study design:

Single centre, prospective randomised, double-blind, controlled trial.

Study population:

Paediatric patients, aged \geq 6 months and \leq 12 years, scheduled for surgical procedure requiring general anaesthesia supplemented with caudal analgesia.

Intervention:

In patients randomised to the intervention group of the trial, the anaesthetic agent sevoflurane will be titrated according to the typical DSA pattern for GA with sevoflurane, provided by the NarcotrendTM.¹ In patients randomised to the control group, sevoflurane will be titrated according to a Minimal Alveolar Concentration (MAC) of 0.9 respectively an end tidal sevoflurane concentration of 2.3% based on standard practice in our paediatric anaesthesia department.

Main study parameters/endpoints:

The speed of emergence from GA (time interval from discontinuation of hypnotic agent until criteria for transfer from the operation theatre to the recovery room are met) is the primary

objective of this trial. Secondary objectives of this trial are the time until discharge criteria from the recovery room are met, the incidence of postoperative delirium, the difference in intra-operative blood pressure between the intervention group and the control group, the incidence of recall of intraoperative events, adverse events and DoH during GA (as measured by the Narcotrend monitorTM).

Nature and extent of the burden and risks associated with participation, benefit and group relatedness:

In patients randomised to the intervention group, the anaesthetic agent sevoflurane will be administered on the basis of objective measures of anaesthetic depth, the typical DSA pattern for GA. We expect a significantly faster speed of emergence and recovery based on clinical experiences with the use of DSA. The NarcotrendTM monitor is validated for use in paediatric patients. There are thus no additional risk factors apart from those, which are inherent with general anaesthesia. Patient randomised to the control group will receive standard treatment, that is delivery of sevoflurane based on a MAC of 0.9 respectively an end tidal sevoflurane concentration of 2.3%.

A non-invasive therapeutical intervention (DSA based conduct of GA) should result in the advantage of faster recovery, without any additional risk factor.

1. INTRODUCTION AND RATIONALE

1.1 General introduction

EEG-based depth of hypnosis (DoH) could result in a faster recovery after the procedure, compared to a standard anaesthesia regimen. A faster recovery could result in advantages for the patient, advantages for the health care providers (enhanced workflow) and an advantage on the environmental impact (less volatile anaesthetic exposure).²

Earlier performed studies with a processed EEG device as the Narcotrend index monitor showed this effect of DoH monitoring in a faster recovery after the procedure.³

However the use of processed EEG monitoring in infants or young children is limited, because of the limitations of the monitors with the variability in age related EEG expression and the anaesthesia specific EEG features.⁴

In density spectral array, these limitations are less relevant due to age and anaesthesia specific EEG expression of the density spectral array pattern.^{1,5,6} Therefore, we think density spectral array would be a more reliable way of monitoring depth of hypnosis in children.

To investigate the additional value of density spectral array in children we have to perform this randomized controlled trial that will investigate the influence of DSA monitoring during general anaesthesia (GA) on the speed of recovery after the procedure, compared to standard general anaesthesia management.

1.2 Density spectral array monitoring

Electroencephalographic density spectral array (DSA) is a three dimensional method to display electroencephalogram (EEG) signals consisting of the EEG frequency (y-axis), the power of the EEG signal (colour-coded to be integrated into a two dimensional plot) and the development of the EEG power spectrum over time (x-axis) (see figure 1).⁷

[figure not shown]

Figure 1 density spectral array (DSA)

Density spectral array has been developed to facilitate the interpretation of unprocessed electroencephalogram signals. It has multiple advantages compared to the widely used electroencephalogram-based indices, or processed EEG monitors.

Electroencephalographic density spectral array shows age-dependent changes in EEG effects of general anaesthetics in children. These age-related changes likely reflect ongoing development within the brain.^{5,6,8}

Furthermore, we know that different anaesthetics act at different molecular targets and neural circuits. This results in anaesthetic drug specific EEG signatures that are readily visible in DSA.⁷ The index-based indices, or processed EEG monitors assume the same index value defines the same level of unconsciousness for all anaesthetics.

Because of the limitations of processed EEG monitors, recently published articles emphasize the use of raw or “unprocessed” EEG monitoring as DSA in the measurement of depth of hypnosis.^{4,9}

We previously performed some observational studies to investigate the specific anaesthetic drug and age-dependent DSA signatures in children.^{1,10} A specific DSA pattern of general anaesthesia with sevoflurane in children aged 6 months to 12 years exists of the appearance of high delta and alpha power on the spectrogram.¹

1.3 General anaesthesia supplemented with caudal analgesia

According to standard care, at Erasmus MC Sophia Children’s Hospital many surgical procedures are performed under general anaesthesia supplement with caudal analgesia. To exclude the impact of opioids on speed of recovery, we choose to include patients undergoing a surgical procedure requiring general anaesthesia supplemented with caudal analgesia.

1.4 Sevoflurane anaesthesia

At ErasmusMC Sophia Children’s Hospital many surgical procedures are performed under general anaesthesia with the volatile anaesthetic sevoflurane. This anaesthetic drug is used for induction and maintenance of general anaesthesia. The concentration sevoflurane is titrated according to age and clinical status of the patient. The minimum alveolar concentration (MAC) is a widely used tool in titrating the surgical level of anaesthesia when DoH monitoring is not used. The MAC value changes with age, where MAC decreases with increasing age. The average MAC concentration of sevoflurane used in the ErasmusMC Sophia Children’s Hospital is 0.9 respectively an end tidal sevoflurane of 2.3%.^{11,12}

1.5 Post-anaesthesia discharge criteria – The Steward Post-Anaesthetic Recovery Score

The 'Simplified Post-Anaesthetic Recovery Score', published by Steward¹³, is the golden standard for assessment of recovery from Anaesthesia:

Consciousness	Score
Awake	2
Responds to stimuli	1
Not responding	0
Airway	
Cough on command or cry	2
Maintaining good airway	1
Requires airway assistance	0
Motor	
Moves limbs purposefully	2
Non-purposeful movement	1
Not moving	0

1.5.1 Discharge criteria from the operating room

The patient is ready to be transferred from the operating room (OR) to the recovery room when the following criteria are met:

- Responding to stimuli (domain Consciousness) **Score ≥ 1**
- Maintaining good airway (domain Airway) **Score ≥ 1**
- Non-purposeful movements (domain Movement) **Score ≥ 1**

That corresponds with a total Steward Score of ≥ 3 .

1.5.2 Discharge criteria from the recovery room

Complete recovery from general anaesthesia is the prerequisite for discharge from the recovery room. It is achieved when the patient meets the following criteria:

- Awake (domain Consciousness) **Score 2**
- Coughing on command or crying (domain Airway) **Score 2**
- Moving limbs purposefully (domain Movement) **Score 2**

That corresponds with a total Steward Score of 6.

1.6 Previous research related to this topic and significance of the project

By now only a limited number of paediatric trials have been published about DSA guidance during general anaesthesia. None of them focused on the speed of recovery after general anaesthesia with DSA.

Based on clinical experience with DSA guided anaesthesia, we expect the use of DSA will result in a faster recovery after general anaesthesia. However, the speed of emergence has never been investigated in previous trials demonstrating the use of DSA in children.

2. OBJECTIVES

Primary Objective: the influence of density spectral array monitoring with the Narcotrend™ monitor on the speed of emergence from general anaesthesia with sevoflurane. The speed of emergence is defined as the time interval between the end of hypnotic drug application and the moment when discharge criteria from the operating room are met (defined as a Steward score ≥ 3).

Secondary Objectives:

- Total time from discontinuation of anaesthetic drug delivery until discharge from the post anaesthesia care unit.
- The incidence of postoperative delirium by the Cornell Assessment of Postoperative Delirium (CAPD) score.^{14,15}
- The difference in intra-operative blood pressure between the intervention group and the control group.
- Differences of depth of hypnosis during the procedure, as measured by the Narcotrend monitor™.
- Incidence of recall of events during the procedure (awareness)
- Adverse events

3. STUDY DESIGN

Single centre, prospective, randomized, double blind trial.

In paediatric patients, aged 6 months until 12 years, scheduled for a surgical procedure which requires general anaesthesia supplemented with caudal analgesia. General anaesthesia is either guided by density spectral array or by a minimal alveolar sevoflurane concentration of 0.9 respectively an end tidal sevoflurane concentration of 2.3%.

The two study groups are compared with respect to the speed of recovery (primary objective). Secondary objectives of this trial are total time from discontinuation of anaesthetic drug delivery until discharge from the post anaesthesia care unit, the incidence of postoperative delirium, the difference in intra-operative blood pressure between the intervention group and the control group, differences of depth of hypnosis during the procedure, as measured by the Narcotrend monitorTM, the incidence of recall of events during the procedure (awareness) and adverse events.

4. STUDY POPULATION

4.1 Population (base)

Paediatric patients, aged 6 months until 12 years, scheduled for a surgical procedure which requires general anaesthesia supplemented with caudal analgesia. The average annual caseload of 400 surgical procedure requiring general anaesthesia supplemented with caudal analgesia at Sophia Children's Hospital indicates that it should be possible to recruit enough patients for this study in a reasonable period of time (approximately 18 months).

4.2 Inclusion criteria

In order to be eligible to participate in this study, a subject must meet all of the following criteria:

- Written informed consent of the parents/legal representatives
- Age > 6 months and < 12 years
- Surgical procedure requiring GA supplemented with caudal analgesia
- Ability of the parents or legal guardians to communicate in Dutch

4.3 Exclusion criteria

A potential subject who meets any of the following criteria will be excluded from participation in this study:

4.3.1 primary exclusion criteria

- Withdrawal of informed consent
- (Chronic) use of drugs influencing the electroencephalogram
- Use of premedication
- Known intolerance for sevoflurane
- Parents/legal guardians unable to communicate in Dutch

4.3.2 secondary exclusion criteria

- protocol violation
- data registration failure

[figure not shown]
4.4 Sample size calculation

There are no previous studies about DSA and the speed of recovery after general anaesthesia.

Based on clinical experience we expect a medium to large effect size so we performed a power analysis using G* power software package with an effect size d of 0.6. The Wilcoxon-Mann-Whitney test was used as statistical test. A sample size of 51 patients per study group is required to achieve a power of 0.9 with an alpha error probability of 0.05.¹⁶ In order to compensate for possible dropouts due to protocol violation or data registration failure a total of 56 patients will have to be included in either group (+10%).

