8.5 Replacement of individual subjects after withdrawal

In order to compete with possible dropouts, due to withdrawal for whatever reason or due to protocol violation, the sample size of the study is about 10% in excess of the results of the sample size calculation. In paediatric depth of anaesthesia studies dropout rates are usually within the range of +/- 5% and mostly due to equipment failure. As a consequence of secondary exclusion due to protocol violation or data registration failure, we choose to increase the number of subjects with 10% on beforehand. There is no need to replace individual subject after withdrawal.

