10. STATISTICAL ANALYSIS

10.1 Primary study parameter(s)

The time interval between the end of anaesthetic drug application and the moment when discharge criteria from the operating room are met (Steward score ≥ 3) is compared between the study groups. Therefore datasets will first be tested for normality by means of the Shapiro-Wilk normality test. As appropriate, either a Mann-Whitney-U-test or a t-test will be performed.

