13.2 Synthesis

Only paediatric patients who are scheduled for a surgical or urological procedure requiring general anaesthesia supplemented with caudal analgesia, aged 6 months until 12 years, are eligible to be included in this study. Participants of this study will not be exposed to an increased risk compared to the (negligible) risk of GA.

The aim of this trial is to investigate if there is a significant benefit of DSA guided GA compared to GA guided by MAC and assessment of clinical signs of hypnotic depth. Based on our personal experience we expect that DSA guidance will result in a faster recovery. We do not expect any negative effects of DSA guidance of GA.

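### The 51 per group matches a one-sided 5% test that the plan never declares; a two-sided 5% test has about 83% power under the same assumptions, not 90%

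*Combined protocol and SAP*

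**What the plan says.** Section 4.4 reports that no earlier study exists, takes d = 0.6 from clinical experience, names the Wilcoxon-Mann-Whitney test and G*Power, and concludes that "51 patients per study group is required to achieve a power of 0.9 with an alpha error probability of 0.05". It then adds 10% for dropouts, giving 56 per group. The number of sides and the parent distribution that the G*Power routine asks for are not given.

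The analysis text does not supply them. Section 10.1 compares the emergence time between groups after a Shapiro-Wilk check: "As appropriate, either a Mann-Whitney-U-test or a t-test will be performed". Section 2 sets the primary objective as "the influence of density spectral array monitoring" on speed of emergence. Section 3 says "The two study groups are compared with respect to the speed of recovery (primary objective"). None of these has a direction.

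Directional language appears elsewhere. The Summary says "We expect a significantly faster speed of emergence and recovery based on clinical experiences with the use of DSA", Section 1.6 repeats the expectation, and Section 13.2 gives the aim as to "investigate if there is a significant benefit of DSA guided GA".

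**The concern.** A significance level of 0.05 with no further comment is ordinarily read as two-sided, and a comparison worded without direction is ordinarily tested that way. The stated sample size fits that reading badly, because it is what a one-sided calculation returns. Either the calculation and the analysis use different error rates, or a one-sided primary test is intended and has not been declared.

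Both readings matter. If the test is two-sided, the trial is more likely to miss the assumed effect than the protocol says. If it is one-sided at 5%, the 90% power stands, but the chance of falsely claiming benefit is 5%, against 2.5% in that direction under a two-sided 5% test. A two-sided p-value between 0.05 and 0.10 in the expected direction would be a success under one reading and a failure under the other. While the plan is silent, that choice could be made after the data are seen.

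**Working it through.** **Inputs.** From Section 4.4: d = 0.6, alpha = 0.05, power = 0.90, Wilcoxon-Mann-Whitney test, 51 per group (56 enrolled). From Section 8.5: usual dropout of about 5%, with 10% allowed for. Assumed because not stated: the number of sides and the parent distribution; each option is tried.

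**Formula.** The asymptotic relative efficiency (ARE) method for the rank test uses an effective group size n' = n × ARE, with df = 2n' − 2 and noncentrality d × √(n'/2) in a noncentral t distribution. The ARE is 3/π for a normal parent, 0.864 for the minimum, π²/9 for logistic and 1.5 for Laplace. ARE = 1 gives the t-test.

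**Reproducing 51.** With a normal parent, n' = 51 × 3/π = 48.70, df = 95.40 and noncentrality = 0.6 × √(48.70/2) = 2.961.

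- One-sided 5%: critical t = 1.661, power = 0.902. At 50 per group the power is 0.897, so 51 is the smallest n that reaches 90%.
- Two-sided 5%: critical t = 1.985, power = 0.834.

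**Required n per group for 90% power at d = 0.6, and two-sided power at 51:**

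| Setting | n, one-sided | n, two-sided | Two-sided power at 51 |
|---|---|---|---|
| Rank test, normal parent | **51** | 63 | 0.834 |
| Rank test, minimum ARE | 56 | 69 | 0.795 |
| Rank test, logistic | 45 | 55 | 0.882 |
| Rank test, Laplace | 33 | 40 | 0.958 |
| t-test | 49 | 60 | 0.851 |

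Only one cell gives 51.

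**Does the dropout allowance help?** Two-sided rank test, normal parent:

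- all 56 analysed: 0.867
- 5% lost (56 × 0.95 ≈ 53): 0.848
- 10% lost (56 × 0.90 ≈ 50): 0.827

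The two-sided t-test gives 0.882 with all 56 analysed, still below 0.90.

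**Effect detectable with 90% power**, two-sided rank test, normal parent: d = 0.66 at 51 and d = 0.63 at 56 (0.664 and 0.633 to three decimals).

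**Simulation check** of the Mann-Whitney test (20,000 trials, normal outcome): at 51 per group, power 0.900 one-sided and 0.833 two-sided. Two-sided power was 0.861 at 56 and 0.905 at 63.

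**Skewed outcome** (assumed lognormal, log-SD 0.3 and 0.5, raw-scale d = 0.6, 51 per group, two-sided): 0.853 and 0.893 if the effect is proportional; 0.889 and 0.950 if it is a pure shift.

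**The case against.** The strongest reply is that this is an omission, not an error. Every input printed in Section 4.4 is consistent with 51, and no section says the test is two-sided. The text leans one way: the Summary says monitoring should speed emergence and that the trial will address this, and Section 13.2 speaks of benefit. One-sided planning is therefore a coherent reading, and under it the 90% is right. That is true, and it is why the fix below leaves a one-sided route open. But an expected direction does not declare a one-sided test, and the three places that define the comparison (Sections 2, 3 and 10.1) carry no direction.

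A second reply is that 83% pairs a rank test with normal data, whereas Section 10.1 would send data that look normal to the t-test. This stands in part. For normal data the t-test figures, 0.851 at 51 and 0.882 at 56, are the more relevant, and both fall short. For non-normal data the two-sided rank-test power at 51 runs from about 0.80 to 0.96 depending on shape, so 90% is attainable under some shapes. The plan assumes none of them, and none of the non-normal parents tried returns 51.

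A third reply is that d = 0.6 is itself a guess, and a modestly larger effect restores 90%. That is also true, but uncertainty about d does not settle which error rates the primary test is meant to have.

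**Conclusion.** The concern holds. The 51 per group is matched exactly by a one-sided 5% rank test with a normal parent, and the plan nowhere declares such a test. Under the same assumptions a two-sided 5% test has 83.4% power at 51 and 86.7% at 56, a shortfall of 6.8 points (90.2 − 83.4) from the calculation that reproduces 51. Reaching 90% two-sided takes 63 analysed per group for the rank test or 60 for the t-test.

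Two assumptions carry this. The one-sided setting is inferred from the arithmetic, since the protocol does not state it. The 83% depends on the normal parent that reproduces 51; other shapes move it in either direction. That the sidedness of the primary test is undeclared depends on neither assumption.

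**What to change.** State in Sections 4.4 and 10.1 that the primary test is two-sided at 0.05. In Section 4.4 also name the parent distribution and restate the power, for example:

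> Assuming a normal parent distribution, 51 analysed patients per group give about 83% power (87% if all 56 are analysed) for d = 0.6, or 90% power for d = 0.66, with a two-sided test at 0.05. For the t-test the power at d = 0.6 is about 85% and 88% respectively.

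If a one-sided test was intended, declare and justify it in both sections before unblinding.

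The cost is about two sentences and a less favourable stated power. The planned tests, the data and the number of patients do not change if the lower power is accepted. Keeping 90% two-sided at d = 0.6 would take 63 analysed per group for the rank test under a normal parent. With the plan's 10% allowance that is 63 × 1.10 = 69.3, so 70 enrolled per group in place of 56.

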5. TREATMENT OF SUBJECTS

The effect of DSA on recovery of anaesthesia in children protocol

Standard anaesthesia monitoring is used during the procedure, ECG, pulse-oxymetry, capnometry and non-invasive measurement of blood-pressure.

Patients randomized to the control group are also attached to the Narcotrend monitor, but with the screen of the monitor obscured. The electroencephalographic data will later be compared to the data of the intervention group in order to assess for differences of depth of hypnosis during the procedure.

After complete recovery from GA, the day thereafter and two weeks later, parents or legal guardians will be contacted via telephone for a systematic interview with the patient if aged > 6 years. This systematic interview is the “Modified Brice-interview”, which is the golden standard for the detection of recall of intraoperative events.^{17,18} Brice interviews will only be performed in patients of at least 6 years of age, because it is known that interviews taken in children of younger ages are likely not to provide the interviewer with reliable information. At the end of the procedure, sevoflurane will be stopped and washed out with 10L flow, FiO₂ 0.5. The patients will be otherwise left undisturbed on the operation table. The sound level in the operation theatre will be reduced to a minimum.

The speed of emergence and recovery will be assessed with the Steward Recovery Score from Anaesthesia.¹³

The incidence of postoperative delirium will be assessed with the Cornell Assessment of Postoperative Delirium (CAPD).^{14,15}

